5.1 Inclusion Criteria

Subjects are eligible to be included in the study only if all of the following criteria apply:

1. Adolescent or adult subject aged 12 – 65 years.
2. Able to understand and give documented informed consent if an adult/parent/guardian and able to understand and provide assent if a minor (age 12-17).
3. Diagnosis of AD according to the Hanifin and Rajka criteria [[Appendix 5, Section 10.5](#)].
4. AD disease duration of at least 6 months, with no change in treatment or severity for at least 4 weeks prior to screening.
5. Overall IGA score of 2 (mild) or 3 (moderate) at baseline on a 5-point IGA scale.

6. TBSA affected of between 2 and 30% at baseline.
7. EASI \geq 5 at baseline.

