2.4.2 Evaluations – Efficacy

2.4.2.1 Eczema Area Severity Index

The EASI is a scoring system that measures 4 clinical signs, the extent of BSA involved, over 4 separate areas (head/neck, trunk, upper extremities, and lower extremities). Total EASI scores range from 0 to 72.

The 4 clinical signs are:

- Erythema
- Induration/papulation
- Excoriation
- Lichenification

And each feature is graded for each region on a 4-point severity scale of 0 to 3, as below, with:

- 0 = absent
- 1 = mild

- 2 = moderate
- 3 = severe

Half-point scores of 1.5 and 2.5 can also be reported. The investigator or qualified assessor will enter the value for erythema, induration/papulation, excoriation and lichenification and extent of BSA for each region on the electronic case report form (eCRF) page. The EASI score will be calculated by the sponsor/designee. The formulation of the score is as shown below:

Eczema Area and Severity Index (EASI) case report form - age ≥ 8 years

Area of involvement: Each body region has potentially 100% involvement. Score 0 to 6 based on the following table:

% involvement	0	1-9%	10 - 29%	30 - 49%	50 - 69%	70 - 89%	90 - 100%
Region score	0	1	2	3	4	5	6

Severity of Signs: Grade the severity of each sign on a scale of 0 to 3:

0	None
1	Mild
2	Moderate
3	Severe

- ✓ Take an average of the severity across the involved area.
- ✓ Half points (1.5 and 2.5) may be used. 0.5 is not permitted – if a sign is present it should be at least mild [1]

Scoring table:

Body region	Erythema (0-3)	Edema/Papulation (0-3)	Excoriation (0-3)	Lichenification (0-3)	Region score (0-6)	Multiplier	Score per body region
Head/neck	(+)	+	+)	X	X 0.1	
Trunk	(+)	+	+)	X	X 0.3	
Upper extremities	(+)	+	+)	X	X 0.2	
Lower extremities	(+)	+	+)	X	X 0.4	
The final EASI score is the sum of the 4 region scores:							_____
							(0-72)

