3.6.1 EASI Analyses

For each visit (baseline, Day 15, Day 29), the following analyses will be performed. All analyses will be based on the ES.

- Descriptive statistics (n, mean, Std Dev, median, minimum, and maximum) will be provided for the per-subject EASI total score (continuous), change from baseline, and percent change from baseline in EASI total score.
- Descriptive statistics (n, %) will be provided for the number and percentage of subjects who achieve EASI-50 (i.e., ≥50% reduction from baseline) and EAST-75 (i.e., ≥75%).

Descriptive statistics (n, mean, Std Dev, median, minimum, and maximum) will be provided for the per-subject EASI by region (head, trunk, upper extremity [UE], lower extremity [LE]), change from baseline, and percent change from baseline values. Treatment group comparisons

in percent change from baseline in EASI total score will be analyzed using a mixed model for repeated measures (MMRM). The model will include fixed effect for study treatment (TER-101 2.75%, vehicle), visit day (Day 15, Day 29), and treatment-by-visit interaction, with visit as the repeating factor, subject nested within the investigational site as a random effect, and baseline score as a covariate. The variance-covariance matrix will be assumed to be unstructured. If the procedure does not converge then the replacement of variance-covariance matrix will be explored in the order of Toeplitz, first-order autoregressive, compound symmetric. The treatment p-value (TER-101 2.75% vs. vehicle), treatment difference, and 95% confidence limits from the model will be presented for the percent change from baseline in EASI at Day 29. Similarly, the treatment difference (TER-101 2.75% vs. vehicle) and 95% confidence limits will be presented for Day 15 as well. Line graphs of least squares mean in percent change from baseline of EASI scores will be presented for Day 15 and Day 29. These treatment group comparisons will be repeated for the PPES.

The following sensitivity analyses will be conducted for the percent change from baseline in EASI total score at Day 29 to explore the impact of dropouts and missing data at Day 29.

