- Last value carried forward (LOCF): for timepoint Day 29, if missing, the last available post baseline EASI total score will be carried forward to the timepoint. After this imputation, an analysis of covariance (ANCOVA) will be used for analyzing the treatment effect at Day 29. The treatment group will be the fixed effect and baseline score will be the covariate. The treatment difference, 95% confidence limits, and p-value will be presented.
- Return to baseline: missing Day 29 value will be imputed based on the baseline value for the patient, with variance adjustment of the Day 29 EASI total score. That is, the missing data will be imputed with values from Normal distribution $N(\text{baseline}_i, \sigma_k^2)$; i = i th subject, where σ_k^2 is the variance estimate of treatment k at Day 29. Five hundred (500) imputation will be implemented. ANCOVA model will be used for each imputation. The results from all imputed datasets will be combined using Rubin's combination rule (PROC MIANALYZE).

In addition, the percent change from baseline in EASI scores and the absolute change from baseline in EASI total score by each region will be analyzed using the MMRM model, as described above. In each case, the treatment p-value (TER-101 2.75% vs. vehicle), treatment difference, and 95% confidence limits from the model, will be presented.

The effect of treatment on response rates (EASI-75, EASI-50) at each visit will be evaluated using a logistic generalized linear mixed model (GLMM) for binary data. The model will include fixed effect for treatment, visit and treatment-by-visit interaction, with subject nested within the investigational site as a random effect. The treatment p-value (TER-101 2.75% vs. vehicle), treatment odds ratio, and 95% confidence limits from the model, will be presented. [Note: In the event of model non-convergence, the response proportions will be analyzed using the Cochran-Mantel-Haenszel test, stratified by baseline IGA.] Bar charts of the response rates at Day 15 and Day 29 will be presented by treatment groups for each response rate (EASI-75, EASI-50).

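### The return-to-baseline imputation draws Day 29 EASI from an unbounded Normal with an arm-level variance on the raw scale, so some imputed scores are negative and the pooled standard error is inflated

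*SAP*

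**What the plan says.** SAP 3.6.1 specifies two missing-data analyses for the primary endpoint: LOCF with ANCOVA, and return to baseline. The variable analysed in both is percent change: "sensitivity analyses will be conducted for the percent change from baseline in EASI total score at Day 29".

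For return to baseline, a missing Day 29 value is replaced by the subject's baseline "with variance adjustment of the Day 29 EASI total score". In detail, "the missing data will be imputed with values from Normal distribution" with mean baseline_i and variance sigma_k squared, which "is the variance estimate of treatment k at Day 29". Then "Five hundred (500) imputation will be implemented", an ANCOVA is fitted to each completed data set, and "The results from all imputed datasets will be combined using" Rubin's rules.

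The SAP does not say whether sigma_k squared is the raw variance of the arm or a variance conditional on baseline, and it gives no bounds for the draw. SAP 2.4.2.1 states the admissible range: "Total EASI scores range from 0 to 72". Protocol 5.1 admits subjects with a baseline EASI as low as 5. Protocol 9.7 leaves the details of imputation to the SAP.

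**The concern.** There are three linked problems.

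1. **Variance.** The Day 29 variance within an arm is the part explained by baseline plus the part left over. The draw is already centred on each subject's own baseline, so adding the whole arm variance brings in the between-subject part a second time.
2. **Scale.** A single EASI-scale variance is divided by each subject's baseline. The noise in percent change then depends on entry severity, which has nothing to do with uncertainty about the missing value.
3. **Bounds.** An unbounded Normal can give an EASI below 0, which is an improvement of more than 100%.

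This is the only specified analysis that assumes dropouts lose their benefit. Protocol 9.7 expects some informative missingness, from lack of efficacy or adverse events. If the interval is wide because of the imputation rule, a non-significant result could be misread as sensitivity to dropout.

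**Working it through.** **Inputs from the documents.** 60 randomized 1:1, 15% dropout, about 50 completers (SAP 1.2); EASI range 0 to 72; minimum baseline 5; 500 imputations; ANCOVA with baseline as covariate; Rubin's rules. The planning figure reproduces: 60 x 0.85 = 51, and 50 / 0.85 = 58.8, rounded up to 59. No figure is stated for the imputation itself.

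**Assumed inputs.** Neither document gives an SD or an effect size, so ranges are used below.

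**Step 1: negative draws.** P(draw < 0) = Phi(-baseline / sigma).

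| Baseline | sigma 3 | sigma 4 | sigma 5 | sigma 6 |
|---|---|---|---|---|
| 5 | 4.8% | 10.6% | 15.9% | 20.2% |
| 10 | 0.04% | 0.6% | 2.3% | 4.8% |

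At baseline 5 and sigma 2 it is only 0.6%.

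**Step 2: noise in percent change.** The SD of one imputed percent change is 100 x sigma / baseline. With sigma 5 this is 100 points at baseline 5 and 50 points at baseline 10.

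**Step 3: double counting, one scenario.** Take baseline mean 10 and SD 4, with percent-change SD 30. The simulated Day 29 SD was 3.95 and the residual SD given baseline 2.99. Baseline therefore explains (3.95^2 - 2.99^2) / 3.95^2 = (15.60 - 8.94) / 15.60 = 43% of the variance that the plain reading adds around baseline. The imputed scores would have SD sqrt(4^2 + 3.95^2) = 5.6, against 3.95 observed at Day 29 and 4 at baseline.

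**Step 4: standard error, raw against residual variance.** Simulation with 30 per arm, 400 trials per scenario and 100 imputations each. Baseline was 5 plus a gamma variable. Mean percent change was -30 (vehicle) and -45 (active), floored at -100, with 15% missing completely at random.

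| Baseline mean (SD) | % change SD | SE, raw variance | SE, residual variance | Ratio | Negative draws, raw |
|---|---|---|---|---|---|
| 8 (2.5) | 30 | 9.78 | 9.19 | 1.06 | 1.2% |
| 8 (2.5) | 45 | 13.11 | 12.62 | 1.04 | 3.4% |
| 10 (4) | 30 | 10.45 | 9.41 | 1.11 | 2.6% |
| 10 (4) | 45 | 13.79 | 12.94 | 1.07 | 5.1% |
| 13 (6) | 30 | 11.15 | 9.68 | 1.15 | 4.0% |
| 13 (6) | 45 | 14.58 | 13.34 | 1.09 | 6.7% |

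For baseline 10 (4) and percent-change SD 45, the ratio is 11.95 / 11.59 = 1.03 at 5% missing and 15.25 / 13.89 = 1.10 at 25% missing. With residual variance 0.4% to 4.2% of draws are still negative, so changing the variance alone does not remove impossible values.

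**Step 5: standard error against a percent-change draw.** Second simulation: lognormal baselines of at least 5 (mean 9.7, SD 4.0), percent-change SD 40, 30 per arm.

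| Missing | As written | Residual variance, EASI scale | Percent-change scale, floor -100% | As written / percent-change |
|---|---|---|---|---|
| 15% per arm | 12.8 | 11.9 | 11.1 | 1.15 |
| 30% vehicle, 0% active | 12.6 | 11.4 | 10.7 | 1.18 |

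Allowing for rounding of the SEs and small differences between runs, the excess is about 14% to 19%. As a rough outside benchmark that ignores baseline adjustment, 25.5 completers per arm with SD 40 give 40 x sqrt(2 / 25.5) = 11.2. The percent-change draw (11.1) is about as precise as the completers alone; the written rule (12.8) is less precise than leaving the missing subjects out.

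**Step 6: point estimate.** For baseline 10 (4) and percent-change SD 45, the mean estimate was -11.64 with the written draw and -11.60 with baseline simply carried forward. There is no shift of note.

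**The case against.** The strongest reply has four parts.

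- **The variance is not defined as raw.** This stands. A reader might infer that the SAP prescribes the full between-subject variance; it says only that it is the arm's variance estimate at Day 29, and a model-based estimate is possible. But that is not stated either, and the scale and bound problems remain under it.
- **Dropouts gain nothing on average.** This stands. A reader might infer that negative draws credit dropouts with clearance or favour one arm. The draws are symmetric about baseline and averaged over 500 imputations, and the estimate does not move. Nor do these draws enter the EASI-50 and EASI-75 analyses, which SAP 3.6.1 handles with a separate GLMM.
- **The high rates are a corner case.** This stands. The 5% to 20% applies to a subject exactly at the entry limit. Fewer values than the dropout rate suggests may need imputing: Protocol 7.1 and 7.2 seek an early termination visit, SAP 3.1 maps assessments from Day 22 onward to Day 29, and subjects with no post-baseline efficacy assessment leave the efficacy set.
- **Much of the excess over the true sampling error comes from random draws pooled by Rubin's rules.** This stands in part. At 15% missing the written rule gave SEs 19% to 47% above the estimator's sampling SD, but residual-variance draws were also 13% to 28% above. The percent-change draw was above it too: 11.1 against about 10.5 in one run (6%), and 10.9 against about 9.1 in another (20%). Only the difference between draws can be charged to the wording of the SAP.

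**Conclusion.** The point holds as a matter of precision and plausibility, not of bias. Followed as written, the rule produces some impossible scores: about 1% to 7% of imputed values over the populations tried, and 5% to 20% at baseline 5 for a Day 29 SD of 3 to 6. It inflates the pooled SE by about 4% to 15% relative to a residual-variance draw, and by about 14% to 19% relative to a percent-change draw. The SE figures assume 30 per arm, percent-change SDs of 30 to 45 and, for the main comparisons, 15% missing; the second comparison also covers 30% missing on vehicle only. The sizes would be smaller with a small Day 29 SD or few missing values.

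A reader might also infer that the primary result is at risk, or that this is the designated conservative analysis. Neither is supported. The primary MMRM, its per-protocol repeat and the LOCF analysis do not use these draws, and the SAP says only that the sensitivity analyses explore the impact of dropout and missing data. The trial is exploratory, with unadjusted p-values. The change should be made because it is cheap and this is one of only two missing-data checks.

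**What to change.** Replace the imputation rule in SAP 3.6.1 as follows.

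- Impute on the analysis scale: percent change at Day 29 from a Normal with mean 0 and variance equal to the residual variance of observed Day 29 percent change given baseline within arm k.
- Set any draw below -100% to -100%. With SD 40 this raises the imputed mean by 40 x [phi(2.5) - 2.5 x (1 - Phi(2.5))] = 40 x (0.0175 - 0.0155) = 0.08 points, which is negligible. Redrawing instead would raise it by 40 x phi(2.5) / Phi(2.5) = 0.7 points.
- Keep the 500 imputations, the ANCOVA and Rubin's rules.
- State that Rubin's variance remains somewhat conservative under this kind of imputation, so that the interval is read accordingly.

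Do not instead truncate EASI-scale draws at 0. Truncation raises the imputed mean by sigma x phi(baseline / sigma) / Phi(baseline / sigma). At baseline 5 that is 6% of baseline for sigma 3, 16% for sigma 4 and 42% for sigma 6, so it is no longer a return to baseline. With 30% missing on vehicle and none on active, it moved the simulated estimate about 1 point towards the drug (-22.9 against -21.9).

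The cost is a few sentences in the SAP and a small programming change, to be made before unblinding. No data collection changes.

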9.7 Handling of Missing Data

All possible efforts will be made to ensure that subjects complete study treatments and all the required assessments. However, in the rare case of subjects discontinuing from study treatment or discontinuing from the study, all attempts will be made to perform all efficacy and safety assessments at the time of discontinuing study treatment or study in order to minimize missing data.

The number of subjects with missing efficacy data at Day 15 and Day 29 visits will be presented as missing for TER-101 or vehicle, together with a summary of the reasons for the missing data. Missing efficacy data will be classified as missing at random (not informative) or missing not at random (informative eg, due to treatment-related discontinuation such as lack of efficacy or an AE), and documented prior to database lock and unblinding.

As missing efficacy data may potentially bias the outcome of the statistical analyses and the subsequent estimation of the magnitude of the treatment effect, different strategies will be applied to provide a balanced assessment of treatment efficacy. The handling of missing data, including consideration of imputing values for missing data, for each efficacy endpoint and sensitivity analyses will be detailed in the SAP prior to the study database lock and unblinding.

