1 STUDY OBJECTIVES AND SAMPLE SIZE RATIONALE

1.1 STUDY OBJECTIVES

TER-101 is a cytosolic phospholipase A2 alpha (cPLA2 α) inhibitor currently in development for the treatment of inflammatory skin diseases, including atopic dermatitis (AD). This Phase 2a study is to assess efficacy, safety, and tolerability of TER-101 (2.75% weight for weight [w/w]) ointment (TER-101 Ointment) with its vehicle (TER-101 Placebo Ointment) twice daily for 28 days in adult and adolescent subjects with mild to moderate AD. Primary and Secondary Objectives are summarized below.

OBJECTIVES	ENDPOINTS
Primary	

 To assess the efficacy of TER-101 (2.75% w/w) ointment vs. vehicle in subjects aged 12 – 65 with mild to moderate AD 	
Primary Efficacy Endpoints
 
 Percent change in EASI from baseline at Day 29 
Secondary Efficacy Endpoints
 
 Percent change in EASI from baseline over time 
 Percent change in EASI by region (head, trunk, UE, LE) from baseline over time EASI-75, EASI-50 responder analysis over time Absolute change in EASI from baseline over time Change in IGA from baseline over time 
 Change from baseline WI-NRS at Days 15, 29 (WI-NRS captured on e-diary daily) Responder analysis: Reduction of ≥ 3 in subjects with baseline WI-NRS ≥ 4 Change in TBSA affected from baseline over time
Secondary	

 To assess the safety and tolerability of TER-101 (2.75% w/w) ointment vs. vehicle in subjects with AD 	
 Safety: TEAEs, SAEs, VS, ECGs, laboratories 
 Tolerability: Scored by investigator at baseline and post-baseline visits on 4-point scale (0 = none; 3 = severe) to include subscores for erythema, burning/stinging, pruritus.

 To assess systemic exposure to TER-101 (2.75% w/w) ointment after BID treatment for 28 days 	PK: systemic plasma trough levels of TER-101 on Days 15, 29

BID = twice daily; EASI = Eczema Area and Severity Index; EASI-50/75 = 50 or 75% reduction in EASI score from baseline; ECG = electrocardiogram; IGA = Investigator Global Assessment; LE = lower extremities; PK =

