3.1 GENERAL STATISTICAL CONSIDERATIONS

Descriptive statistics (mean, standard deviation [Std Dev], median, minimum, and maximum) will be used for continuous variables; number and percentage of subjects will be used for discrete variables. In general, the last measurement prior to the first dose of study treatment will be used as the baseline value with exception of WI-NRS, where the score recorded on Day 1 describing the worst itch score 24 hours prior will be used as the baseline. Nominal visits will be used for by-visit summaries and analyses for safety evaluations (i.e., laboratory sampling, physical examinations, vital signs, and electrocardiogram). For efficacy evaluations of EASI, IGA, and TBSA, analysis visits will be used for by-visit summaries. Analysis visits are defined as below:

Analysis Visit*	Target Day	Range
Day 8	Day 8	Day 2 – Day 11
Day 15	Day 15	Day 12 – Day 21
Day 29	Day 29	≥Day 22

* If there are multiple observations in the range, then the record collected closest to the target day will be selected; if there are multiple observations that have equal distance from the target day, the latter one will be used.

All treatment group comparisons will be made at the 0.05 level using a two-sided hypothesis test, unless otherwise specified. Given the exploratory nature of this study, p-values from all significance tests will be reported without adjustment for multiplicity.

Summaries will be presented by each treatment group, ie, TER-101 2.75% ointment, Vehicle ointment.

All tabulations of summary statistics, graphical presentations, and statistical analyses will be performed using SAS[®] Version 9.4 or higher.

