3.2 ANALYSIS POPULATION AND DISPOSITION OF SUBJECTS

3.2.1 Data Sets Analyzed

For purposes of analysis, the following populations are defined

Population	Description
Efficacy analysis set (ES)	All randomized subjects who receive at least 1 application of the study treatment and have at least 1 post-baseline efficacy assessment. The treatment group as assigned (randomized to) will be used for analyses.
Per protocol efficacy analysis set (PPES)	All subjects in ES without major protocol deviations that impact the interpretation of the results. The treatment group for the first application will be used for analyses.
Safety analysis set (SS)	All randomized subjects who receive at least 1 application of the study treatment. If any TER-101 was applied, then the subject will be summarized under TER-101 treatment group.
PK analysis set (PKS)	All subjects in SS with at least 1 blood draw to measure TER-101.

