3.6 EFFICACY ANALYSIS

All efficacy analyses and summaries will be performed on the ES by randomized treatment group. Additional analyses based on PPES will be specifically mentioned.

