4 CHANGES TO PLANNED ANALYSES

Due to the small sample size of the study and the infrequent assessment of response over time, the Kaplan-Meier (KM) analysis of time to onset of response (EASI-75, EASI-50) will not be conducted.

Because the change from baseline in the IGA is expected to take on a limited set of values, it will be considered as ordinal data rather than a continuous variable, and thus will be analyzed using a generalized linear model for repeated ordinal data.

The change in individual components of EASI (erythema, edema/papulation, excoriation, lichenification) by visit will not be analyzed, only EASI by region will be analyzed due to limitation in defining EASI score for each sign/symptom.

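### Does the SAP need a rule for regional percent change in EASI when a region is clear at baseline?

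*SAP*

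**What the plan says.** SAP 1.1 lists "Percent change in EASI by region (head, trunk, UE, LE) from baseline over time" among the secondary efficacy endpoints, and Protocol 9.4.3 has the same endpoint.

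SAP 3.6.1 plans descriptive statistics for "EASI by region (head, trunk, upper extremity [UE], lower extremity [LE]), change from baseline, and percent change from baseline values". It later adds that "the percent change from baseline in EASI scores and the absolute change from baseline in EASI total score by each region will be analyzed" with the MMRM used for total EASI, giving a p-value, a treatment difference and 95% confidence limits. SAP 3.6 sets the population: "All efficacy analyses and summaries will be performed on the ES by randomized treatment group". To enter the ES, a treated subject must "have at least 1 post-baseline efficacy assessment" (SAP 3.2.1).

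SAP 4 removes the analysis of individual signs and states that "only EASI by region will be analyzed due to limitation in defining EASI score for each sign/symptom". It says nothing about a region that scores 0 at baseline, and neither do SAP 3.1, 3.2.1 and 3.6.1 or Protocol 9.4.6 and 9.7.

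The EASI scoring table (SAP 2.4.2.1, Protocol 10.6) gives a region with 0% involvement an area score of 0, so its regional EASI is 0. Protocol 5.1 requires total EASI of at least 5 and TBSA of 2 to 30%, and does not require any particular region to be involved.

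**The concern.** Percent change divides by the baseline value. For a subject whose head, trunk, arms or legs are clear on Day 1, that region's percent change is undefined. The SAP nevertheless assigns the analysis to the whole ES and does not say what happens to these subjects.

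Two handlings come to mind: leave the subject out of that region's analysis, or score a region that stays clear as 0% change. They estimate different quantities, so a choice made after unblinding could in principle move four regional treatment differences. The silence stands out more because Protocol 9.7 says the handling of missing data "for each efficacy endpoint and sensitivity analyses will be detailed in the SAP prior to the study database lock and unblinding", and because SAP 4 shows that the authors did consider whether EASI sub-scores are well defined.

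The wording of the MMRM sentence adds to this. The phrase about regions follows the absolute-change clause, so it is not certain that regional percent change is tested as well as described.

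**Working it through.** **The plan's own figure.** About 60 randomized with 15% dropout gives 60 × 0.85 = 51, stated as about 50 completers. In reverse, 50 / 0.85 = 58.8, so 59, stated as about 60. It reproduces. The question here does not depend on it, except that 50 is used below as the number of completers.

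**Can a region be clear in an eligible subject?** Regional EASI = (sum of four sign grades) × (area score) × (multiplier), with multipliers head 0.1, trunk 0.3, arms 0.2 and legs 0.4. For TBSA, assume that each region's share of body surface equals its multiplier. With all four signs moderate (sum 8) and one region involved:

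| Only region involved | Area score (% of region) | EASI | TBSA |
|---|---|---|---|
| Legs | 2 (10–29%) | 8 × 2 × 0.4 = 6.4 | 4–11.6% |
| Arms | 4 (50–69%) | 8 × 4 × 0.2 = 6.4 | 10–13.8% |
| Trunk | 3 (30–49%) | 8 × 3 × 0.3 = 7.2 | 9–14.7% |

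Each row meets EASI ≥ 5 and TBSA 2–30% with three regions at 0. The head alone reaches 8 × 6 × 0.1 = 4.8 at this severity. With one half-point more it reaches 8.5 × 6 × 0.1 = 5.1. With all signs mild (sum 4), trunk and legs at area score 2 give 4 × 2 × 0.3 + 4 × 2 × 0.4 = 5.6, at about 7% TBSA at the lower bounds. So any of the four regions can be 0 in an eligible subject, and the premise holds.

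**What the ordinary handling does.** A zero denominator yields no value, and the record drops out of that analysis. Let p be the share of subjects clear in a region. The number analysed is 50 × (1 − p). With the same standard deviation, the standard error is 1/√(1 − p) times that with all 50.

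| p (assumed) | Number analysed | SE factor |
|---|---|---|
| 20% | 40 | 1/√0.8 = 1.12 |
| 40% | 30 | 1/√0.6 = 1.29 |
| 60% | 20 | 1/√0.4 = 1.58 |

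**Is the remaining comparison sound?**

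- Baseline EASI is an eligibility item that must be confirmed before randomization (Protocol 1.3, 4.1.2 and 5.1). Membership of the subset therefore cannot depend on treatment.
- SAP 3.6.1 includes n in the regional descriptive statistics, and SAP 3.1 adds "Summaries will be presented by each treatment group". The reader will see how many subjects each regional result rests on.
- New lesions in a clear region (Protocol 4.1.3) enter regional absolute change, total EASI and TBSA, which are all defined at a baseline of 0.
- The primary endpoint divides by a total EASI of at least 5.

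**How far would the alternative differ?** Suppose the difference among involved subjects is d = 20 percentage points (assumed), clear regions stay clear, and raw means are compared. Leaving subjects out gives 20 points. Coding them 0% gives (1 − p) × 20 = 16, 12 or 8 points for p = 20, 40 or 60%. These figures are illustrative only, since p and d are assumed and neither document mentions 0% coding. The alternative is also not a complete rule. A region that goes from clear to, say, four mild signs at area score 1 on the legs moves from 0 to 4 × 1 × 0.4 = 1.6, and its percent change is still undefined.

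**The case for a change.** The best case for a change is that it costs one sentence, the rule is absent, and the SAP does state a baseline restriction where it wants one: WI-NRS responders are limited to baseline WI-NRS of at least 4 (SAP 3.6.3). Writing the regional rule down before unblinding would remove any suspicion of choice. The absence and the low cost both stand.

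The rest is weaker. The sentence would record what an analyst would do anyway, so no expected result changes. Appeal to the ES does not create a conflict. ES entry needs only one post-baseline efficacy assessment of any kind, and WI-NRS is recorded daily, so a subject can be in the ES with no post-baseline EASI. EASI models on the ES therefore already use only those subjects who have the values they need.

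Protocol 9.7 does not carry the point either. It is mainly about assessments lost when subjects discontinue. Here both assessments are observed and only the ratio is undefined.

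A rule for exact zeros would also leave the larger weakness of regional percentages untouched. A head score moving from 0.1 to 0.4 is (0.4 − 0.1) / 0.1 = +300%. Regional absolute change, already planned, is the natural check on both.

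The loose wording of the MMRM sentence is a fair remark. SAP 1.1 and the descriptive plan settle that regional percent change is derived, whichever reading is taken. Absolute change in total EASI is a listed endpoint with an MMRM in Protocol 9.4.6, so the sentence should not be read as regional only. Running the model for regional percent change, regional absolute change and total absolute change satisfies every reading.

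**Conclusion.** No change is needed. The SAP is silent on a zero regional baseline, but this is a detail that analysts fill in one sensible way: the undefined value is missing, and that region's percent-change analysis covers subjects involved there at baseline. The result is a valid randomized comparison in a subset whose size is reported, with planned analyses beside it that use regions clear at baseline.

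The cost is some precision in one family of secondary results. If 20 to 60% of subjects are clear in a region, 40 to 20 of 50 completers contribute and the standard error is 1.12 to 1.58 times that with all 50. The study is exploratory, its p-values are unadjusted, and its sample size has no statistical basis, so no decision rule in the plan depends on these results. The primary endpoint is unaffected.

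The conclusion assumes that zero denominators are set to missing and not given a value. The TBSA ranges assume that regional body-surface shares equal the EASI multipliers. The share of clear regions and the 20-point difference are assumptions throughout.
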